#### COVID-19 Pandemic-Related Acceptable Protocol Modifications

In the event that a subject or study personnel cannot come to the site for a study visit requiring a urine pregnancy test because of the COVID-19 pandemic, home pregnancy test kits may be provided to subjects to self-administer at home and report results to study site over the phone. If a urine pregnancy test cannot be completed, the site will need to reach out to the medical monitor to determine further action and if study drug should be discontinued.

#### Urinalysis

Urinalysis will be completed at all required visits. Specified abnormal macroscopic urinalyses defined as leukocytes, nitrite, protein, ketones, or blood greater than negative, or glucose greater than normal will be followed up with a microscopic analysis at the central laboratory.

# 3.20 Subject Withdrawal from Study

All attempts must be made to determine the date of the last study drug dose and the primary reason for discontinuation of study drug or study participation. The information will be recorded on the appropriate eCRF page. However, these procedures should not interfere with the initiation of any new

treatments or therapeutic modalities that the investigator feels are necessary to treat the subject's condition. Following discontinuation of study drug, the subject will be treated in accordance with the investigator's best clinical judgment, irrespective of whether or not the subject decides to continue participation in the study.

## 4 SAFETY MANUAL

## 4.1 Methods and Timing of Safety Assessment

All serious adverse events (SAEs) as well as protocol-related nonserious AEs (e.g., occurrence during Screening) will be collected from the time the subject signed the study-specific informed consent until study drug administration. From the time of study drug administration until 30 days after discontinuation of study treatment, all AEs and SAEs will be collected whether solicited or spontaneously reported by the subject. After 30 days following completion of study treatment and throughout the Post-Treatment Period, all spontaneously reported SAEs will be collected (nonserious AEs will not be collected).

Adverse events of special interest, such as elevated liver transaminases, decreased BMD/ bone fractures, and all mood- and depression-related events, will require additional information, to be collected in the EDC system.

Adverse event information will be collected as shown in Figure 2.

SAEs and Protocol-Related SAEs and Nonserious AEs Nonserious AEs Elicited and/or Spontaneously Reported

Consent Study Drug Study Drug 30 Days After Signed Start Stopped Study Drug Stopped

Figure 2. Adverse Event Collection

AE = adverse event; SAE = serious adverse event

# 4.2 Recording Data and Analyses of Safety Findings

Adverse events will be coded using the Medical Dictionary for Regulatory Activities (MedDRA). The number and percentage of subjects with treatment-emergent AEs (i.e., any event that begins or worsens in severity after initiation of study drug through 30 days post-study drug dosing) will be tabulated by primary MedDRA System Organ Class (SOC) and preferred term (PT) and compared between arms using Fisher's exact test. The tabulation of the number of subjects with treatment-emergent AEs by severity grade and relationship to study drug also will be provided. Subjects reporting more than 1 AE for a given

MedDRA preferred term will be counted only once for that term using the most severe grade according to the severity grade table and the most related according to the relationship to study drug tables. Subjects reporting more than 1 type of event within an SOC will be counted only once for that SOC.

# 4.3 Reporting Adverse Events and Intercurrent Illnesses

In the event of an SAE, whether associated with study drug or not, the investigator will notify Clinical Pharmacovigilance within 24 hours of the site's being made aware of the SAE by entering the SAE data into the EDC system. SAEs that occur prior to the site having access to the RAVE® system, or if RAVE is not operable, should be documented on the SAE non case report forms (CRFs) and emailed (preferred route) or faxed to Clinical Pharmacovigilance within 24 hours of the site's being made aware of the SAE.

Email: [contact]

FAX to: [contact]

For safety concerns, contact the Men's and Women's Health Safety Team at:

Men's and Women's Health Safety Team

[name]

[name]

[name]

Office: [contact]

Email: [name]

For any subject safety concerns, please contact the physician listed below:

Primary Therapeutic Area Medical Director EMERGENCY MEDICAL CONTACT:

Contact Information:

Office: Mobile: Fax:

In emergency situations involving study subjects when the primary TA MD is not available by phone, please contact the 24-hour AbbVie Medical Escalation Hotline where your call will be re-directed to a designated backup AbbVie TA MD:

[contact]

The sponsor will be responsible for Suspected Unexpected Serious Adverse Reactions (SUSAR) reporting for the Investigational Medicinal Product (IMP) in accordance with Directive 2001/20/EC.

## 4.4 Pregnancy

Pregnancy in a study subject must be reported to AbbVie within 1 working day after the site becomes aware of the pregnancy. Information regarding a pregnancy occurrence in a study subject and the outcome of the pregnancy will be collected for any study subject with a positive serum pregnancy test after receiving at least one dose of study drug through 30 days following the last dose of study drug. In the event of a positive urine pregnancy test, while awaiting serum pregnancy test results during the Treatment Period, study drug should be temporarily discontinued.

If the subject has a positive serum pregnancy test during the Treatment or within 30 days following last dose of study drug, no additional study procedures will be conducted. However, an ultrasound examination will be performed (read locally) as early as possible during the first trimester of pregnancy to assess gestational age and document intrauterine pregnancy. The site will follow the course of the subject's pregnancy and report to the sponsor on the health of the subject and fetus at each trimester, the outcome, the newborn at the first post-delivery pediatrician visit, and the infant 6 to 12 months post-delivery. The following information should be collected: fetal outcome (e.g., spontaneous or elective abortion, live infant, or still birth), date and mode of delivery, birth weight, birth length, gender, any congenital anomaly, and medically significant complications during pregnancy or labor or delivery. For live infant births, information on the health of the infant will be collected from the first post-delivery pediatrician visit and at 6 to 12 months after delivery.

#### COVID-19 Pandemic-Related Acceptable Protocol Modifications

Supplemental study case report forms should be completed in the event of COVID-19 related missed/virtual visits, study drug interruptions or discontinuations, or AEs (including capture of specific signs/symptoms of infection and testing results).

COVID-19 infections should be captured as AEs. If the event meets the criteria for an SAE, then follow the SAE reporting directions per the protocol and listed in Section 4.3. The following COVID-19 related supplemental eCRFs should be completed:

- COVID-19 Supplemental Signs/ Symptoms
- COVID-19 Status Form

If a subject has a confirmed or suspected COVID-19 infection and study drug was interrupted, the investigator should contact the sponsor emergency medical contact listed in Section 4.3 before reintroducing study drug.

## 5 COUNTRY-SPECIFIC REQUIREMENTS

## 5.1 SUSAR Reporting

AbbVie will be responsible for SUSAR reporting for the IMP in accordance with global and local guidelines and Appendix A of the Investigator Brochure will serve as the Reference Safety Information (RSI). The RSI in effect at the start of a DSUR reporting period serves as the RSI during the reporting period. For follow-up reports, the RSI in place at the time of occurrence of the 'suspected' Serious Adverse Reaction will be used to assess expectedness.

## 6 STUDY DRUG

## 6.1 Treatments Administered

The study drug (elagolix or matching placebo) will be dispensed in the form of capsules at the visits listed in Section 2.2.

Study drug must not be dispensed without contacting the IRT system. Study drug may only be dispensed to subjects enrolled in the study through the IRT system. At the end of the Treatment Period or at the Premature Discontinuation visit, the site will contact the IRT system to provide visit date information and study drug return information for each kit.

## COVID-19 Pandemic-Related Acceptable Protocol Modifications

In the event that a subject cannot come to the site because of the COVID-19 pandemic, the site may contact the IRT for kit assignment after ensuring subject is eligible to continue with study drug dosing and confirming that a home urine pregnancy test was performed and the result was negative. Study drug dispensing can then be undertaken as outlined in Section 3.18.

# 6.2 Packaging and Labeling

All study drugs will be supplied in blister cards.

Each blister card will be labeled as required per country requirements.

The labels must remain affixed to the kit. Upon receipt, study drug should be stored as specified on the

label and kept in a secure location. Each kit will contain a unique kit number. This kit number is assigned to a subject via IRT and encodes the appropriate study drug to be dispensed at the subject's corresponding study visit. All blank spaces on the label will be completed by the site staff before dispensing to subjects.

#### Storage and Disposition of Study Drug

Elagolix and matching placebo study drug must be stored at controlled temperature 15° to 25°C (59° to 77°F).

The investigational products are for investigational use only and are to be used only within the context of this study. The study drug supplied for this study must be maintained under adequate security and stored under the conditions specified on the label until dispensed for subject use or returned to AbbVie. Returned study drug should not be re-dispensed to the subject.

## 6.3 Method of Assigning Subjects to Treatment Groups

This is a Phase 2, multicenter, randomized, double-blind (sponsor-unblinded), placebo-controlled study. All eligible subjects will receive elagolix or matching placebo.

At the screening visit, all subjects will be assigned a unique subject number through the use of the IRT. For subjects who do not meet the study selection criteria, the site personnel must contact the IRT system and identify the subject as a screen failure.

Subjects who are enrolled will retain their subject number assigned at the screening visit throughout the study. Upon receipt of study drug, the site will acknowledge receipt in the IRT system.

Contact information and user guidelines for IRT use will be provided to each site.

## 6.4 Selection and Timing of Dose for Each Subject

Study drug will be administered at the scheduled visits (Section 2.2) for the randomized subjects. Subjects will be instructed to take study drugs at the same time every day.

Study drug will be provided by AbbVie as capsules in dosages of 25 mg, 75 mg, 150 mg, and placebo capsules.

Study drug will be taken orally as 3 capsules each day.

# APPENDIX A. E-DIARY FOR BLEEDING

Describe your uterine bleeding in the last 24 hours:

- 1. NONE
- 2. SPOTTING (a light amount of bleeding noted, no protection or panty shield only).
- 3. BLEEDING (1 or more tampons or pads required in last 24 hours).

eDiary for Bleeding -English-US-V1

# APPENDIX B. PATIENT GLOBAL IMPRESSION FOR ACNE AND HIRSUTISM

## Patient Global Impression for Acne (PGIA)

Please choose the response below that best describes the overall change in your acne since you started taking the study medication.
□ Much better
□ A little better
□ No change
□ A little worse
□ Much worse
Patient Global Impression for Hirsutism (PGIH)
Please choose the response below that best describes the overall change in your hair growth since you started taking the study medication.
□ Much better
□ A little better
□ No change
□ A little worse
□ Much worse

 $No\ use\ or\ disclosure\ outside\ AbbVie\ is\ permitted\ without\ prior\ written\ authorization\ from\ AbbVie.$

Appendix A. Definition of Adverse Events of Special Interest29

1.0 Introduction

This Statistical Analysis Plan (SAP) describes the statistical analyses for Elagolix Study M16-837 'Phase 2, Multicenter, Double-blind (Sponsor-unblinded), Randomized, Placebo-Controlled Study of the Safety and Efficacy of Elagolix in Women with Polycystic Ovary Syndrome.'

The analyses of pharmacokinetic endpoints, pharmacodynamic endpoints, and biomarkers will not be covered in this SAP.

The SAP will not be updated in case of administrative changes or amendments to the protocol unless the changes impact the analysis.

Unless noted otherwise, all analyses will be performed using SAS Version 9.3 (SAS Institute Inc., Cary, NC 27513) or later under the UNIX operating system.

2.0 Study Design and Objectives

2.1 Objectives

The objective of the study is to assess the pharmacokinetics, pharmacodynamics, safety, and efficacy of elagolix in women with Polycystic Ovary Syndrome (PCOS).

[figure not shown]
2.2 Study Design Overview

This is a Phase 2, randomized, double-blind (sponsor-unblinded), 6-month, placebo controlled, parallel group, multicenter study designed to assess the PK and PD of elagolix and to demonstrate the safety and efficacy of elagolix in women with PCOS.

The duration of the study could be up to 42 weeks, which includes an 8-week Washout (if necessary), a 6-week Screening Period, a 24-week Treatment Period, and a 30-day Post-Treatment Follow-up Period.

The schematic of the study is presented in Figure 1.

Figure 1. Study Schematic

BID = twice daily; M = month; PTFU = post-treatment follow-up; QD = once daily

2.3 Treatment Assignment and Blinding

Stratified randomization will be performed by a ratio of 2:2:2:2:2:3 to the following treatments: 25 mg BID, 50 mg QD, 75 mg BID, 150 mg QD, 300 mg QD, or placebo (20 subjects in each active treatment group and 30 subjects in the placebo group). Subject randomization will be stratified based on Ferriman-Gallwey (FG) score (< 8 , ≥ 8) and body mass index (BMI) (< 30 , ≥ 30).

2.4 Sample Size Determination

The planned total sample size is 130 subjects: 20 subjects per elagolix treatment group and 30 subjects assigned to placebo.

The sample size will provide at least 85% power to detect a difference between each elagolix group and the placebo group in the proportion of menstrual cycle responders based on a Pearson Chi-square test, assuming response rates of 10% for the placebo group and 50% for the elagolix group with 2-sided $\alpha = 0.05$. The above sample size was calculated using nQuery advisor 7.0.

3.0 Endpoints

3.1 Primary Endpoint(s)

The primary endpoint is the proportion of menstrual cycle responders as defined in Section 8.3.1.

3.2 Secondary Endpoint(s)

The secondary endpoint is change from Baseline to Week 1 in the area under the luteinizing hormone (LH) serum concentration-time curve (AUC) as defined in Section 8.4.

3.3 Other Efficacy Endpoint(s)

The primary and secondary efficacy endpoints are listed in Section 3.1 and Section 3.2, respectively. The additional efficacy endpoints are:

- Proportion of complete menstrual cycle responders (normal menstrual cycles by the beginning of Month 3 and maintained thereafter each month through Month 6).
- Change from Baseline in the LH serum AUC at each scheduled assessment during the Treatment Period.
- Change from Baseline in the FSH serum AUC at each scheduled assessment during the Treatment Period.
- Change from Baseline in total and free testosterone serum concentration at each scheduled assessment during the Treatment Period.
- Number of menstrual bleeding episodes during the Treatment Period.
- Number of ovulations based on weekly serum progesterone level during the Treatment Period.
- Proportion of subjects with at least 2 ovulations during the Treatment Period
- Endpoints related to hyperandrogenism – Patient Global Impression (PGI) for both acne and hirsutism; change from Baseline at each scheduled assessment during the Treatment Period for the following: acne measured with total lesion

count and investigator's global assessment (IGA), hirsutism measured with Ferriman–Gallwey (FG) score.

- Endpoints related to metabolic features - change from Baseline at each scheduled assessment during the Treatment Period for the following: glycated hemoglobin (HbA1c), fasting insulin/glucose, body mass index (BMI), lipids, waist circumference.
- Change from Baseline at each scheduled assessment during the Treatment Period for additional hormones: androstenedione, anti-Mullerian hormone (AMH), estradiol (E2), progesterone.
- Change from Baseline in ovarian volume at each scheduled assessment during the Treatment Period.
- Endpoints related to the subject's quality of life: change from Baseline in domains from the Polycystic Ovary Syndrome Questionnaire (PCOSQ) (emotions, body hair, weight, infertility problems, and menstrual problems) and the Menstrual Bleeding Questionnaire (MBQ) at each scheduled assessment during the Treatment Period.

3.4 Safety Endpoint(s)

Safety evaluations include physical examination, vital signs, pelvic ultrasound (transabdominal ultrasound [TAU] and transvaginal ultrasound [TVU]), clinical laboratory tests (including hematology, chemistry, urinalysis, and lipid panel), bone mineral density (BMD) via dual energy X-ray absorptiometry (DXA) examinations, and adverse event (AE) monitoring for the entire study duration.

4.0 Analysis Populations

The following population sets will be used for the analyses.

The Full Analysis Set (FAS) consists of all randomly assigned subjects who have received at least one dose of study drug in this study. The data from the FAS will be presented by the treatment group assigned at the time of randomization, even if the subject does not

receive the correct treatment or does not follow the protocol until completion. The FAS will be used for all baseline and efficacy analyses.

The Safety Analysis Set consists of all subjects who received at least one dose of study drug. The data from the safety analysis set will be presented by the treatment actually received no matter what treatment group was assigned at the time of randomization. If a subject takes more than one treatment, the subject will be analyzed in the safety analysis set as taking the treatment to which she was randomized. All safety analyses will be performed based on the safety analysis set.

5.0 Subject Disposition

The total number of subjects who were randomized and who completed the study will be summarized by treatment group and overall. In addition, reasons for study discontinuation will be summarized.

A summary of subject accountability will be provided where the number of subjects in each of the following categories will be summarized for each treatment group:

- Subjects randomized in the study;
- Subjects who took at least one dose of study drug;
- Subjects who completed protocol-specified treatment;
- Subjects who prematurely discontinued study drug;

The number and percentage of subjects who discontinued study drug will be summarized by treatment group and overall as follows:

- By any reason for discontinuation;
- By primary reason for discontinuation.

In addition, the number and percentage of subjects who discontinued study will be summarized by treatment group and overall as follows:

- By any reason for discontinuation;
- By primary reason for discontinuation.

6.0 Study Drug Duration

For the Safety Analysis Set, duration of treatment will be summarized for each treatment group and for all investigational study drug dose groups combined. Duration of treatment is defined for each subject as last dose date minus first dose date + 1. Duration of treatment will be summarized using the number of subjects treated, mean, standard deviation, median, minimum and maximum. In addition, the number and percentage of subjects in each treatment duration interval (1 – 28, 29 – 56, 57 – 84, 85 – 112, 113 – 140, 141 – 168, and > 168 days) will be summarized.

7.0 Demographics, Baseline Characteristics, Medical History, and Prior/Concomitant Medications

Demographics, baseline or disease characteristics, medical history, and prior and concomitant medications will be summarized by treatment group and overall using the FAS. Categorical variables will be summarized with the number and percentage of subjects; percentages will be calculated based on the number of non-missing observations. Continuous variables will be summarized with descriptive statistics (number of non-missing observations, mean and standard deviation, median, minimum and maximum).

7.1 Demographics and Baseline Characteristics

Continuous demographic variables include age, weight, height, waist circumference, and body mass index (BMI). Categorical demographic variables include sex, ethnicity, race, age (18 – 26, 27 – 35 years), BMI (18.5 – < 25, 25 – < 30, ≥ 30 kg/m²), tobacco use (current, former, never, unknown), and alcohol user (current, former, never, unknown).

Disease characteristics include menstrual and obstetrical history. Continuous variables include number of days bleeding. Categorical variables include cycle length (> 35 days

[yes/no]), typical intensity of menstrual periods (light, moderate, heavy), ever been pregnant (yes/no), and number of pregnancies (0, 1, 2, 3, 4, > 4), and congenital abnormality (yes/no).

7.2 Medical History

Medical history and gynecological medical/surgical history data will be coded using the Medical Dictionary for Regulatory Activities (MedDRA). The actual version of the MedDRA coding dictionary will be noted in the statistical tables and clinical study report. The number and percentage of subjects in each medical history category (by MedDRA system organ class and preferred term) will be summarized by treatment group and overall. The system organ class (SOC) will be presented in alphabetical order, and the preferred terms will be presented in alphabetical order within each SOC. Subjects reporting more than one condition/diagnosis will be counted only once in each row (SOC or preferred term).

7.3 Prior and Concomitant Medications

Prior and concomitant medications will be summarized by generic name.

Prior medications are those medications with a start date prior to the first study drug administration date.

Concomitant medications are those medications taken during the Treatment Period with an end date after the first dose of study drug or ongoing at the end of the study, and a start date prior to the last dose of study drug. A medication will be considered a concomitant medication where one of the following three cases occur (1) the start date is missing and the end date is either after or on the first study drug dose date; (2) the start date is not missing and the end date is missing; (3) both the start date and the end date are missing.

Prior and concomitant medications will be summarized by ATC Classification and preferred terms from the World Health Organization (WHO) Drug Dictionary with number and percentage for each treatment group and overall. A subject who reports two

or more uses of the same medication will be counted only once within each WHO preferred term. A subject with medications with more than one generic name will be counted only once in the overall total.

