## 5.4 Prior and Concomitant Therapy

Any medication administered to treat PCOS symptoms within 6 months prior to Washout or Screening must be recorded in source documents and in the electronic case report forms (eCRFs). The date(s) of administration (including start and stop dates), dose, frequency, route, and reason for use and discontinuation must be recorded in source documents and on the appropriate eCRF.

All other medications or vaccines (including over-the-counter or prescription medicines, vitamins and/or herbal supplements) that the subject is receiving at the time of entering into the Washout Period (if required) or Screening Period and during the Treatment and Post-Treatment Follow-Up Periods must be recorded in source documents and on the Concomitant Medication eCRFs. The reason for use, date(s) of administration (including start and end dates), and dosage information (including dose, frequency and route) must be recorded.

The AbbVie TA MD should be contacted if there are any questions regarding concomitant or prior therapies. Information regarding potential drug interactions with elagolix can be located in the elagolix Investigator's Brochure.

Subjects must be able to safely discontinue any prohibited medications 5 half-lives or up to 8 weeks prior to initial study drug administration. Subjects must be consented for the study prior to discontinuing any prohibited medications for the purpose of meeting study eligibility.

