## 5.6 Follow-Up for Subject Withdrawal from Study

To minimize missing data for efficacy and safety assessments, subjects who prematurely discontinue study drug treatment should continue to be followed for all regularly scheduled visits, unless subjects have decided to discontinue the study participation entirely (withdrawal of informed consent). Subjects should be advised on the continued scientific importance of their data even if they discontinue treatment with study drug early.

If a subject prematurely discontinues study participation (withdrawal of informed consent), the procedures outlined for the Premature Discontinuation visit (PD visit) should be completed as soon as possible, preferably within 2 weeks. In addition, if subject is willing, a 30-day follow-up phone call after the last dose of study drug may be completed to ensure all treatment-emergent AEs/serious adverse events (SAEs) have been resolved.

All attempts must be made to determine the date of the last study drug dose and the reason for discontinuation of study drug or study participation. The information will be recorded on the appropriate eCRF page. However, these procedures should not interfere with the initiation of any new treatments or therapeutic modalities that the investigator considers necessary to treat the subject's condition. Following discontinuation of study drug, the subject will be treated in accordance with the investigator's best clinical judgment, irrespective of whether or not the subject decides to continue participation in the study.

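### SAP 7.3 contradicts itself: case (2) counts as concomitant a medication known to have started after the last dose if its end date is missing, though the definition excludes it

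*SAP*

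**What the plan says.** SAP 7.3 gives two consecutive rules.

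The first is the definition. It begins "Concomitant medications are those medications taken during the Treatment Period with an end date after the first dose of study drug or ongoing at" (quoted up to its reference to study end), and it adds an upper limit: "and a start date prior to the last dose of study drug".

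The second is a list, introduced by "A medication will be considered a concomitant medication where one of the following three cases occur". Case (1) is "1) the start date is missing and the end date is either after or on the first study drug dose date". Case (2) is "2) the start date is not missing and the end date is missing". Case (3) covers records with neither date.

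The SAP does not say which rule prevails. It also does not say whether a medication marked as ongoing counts as having a missing end date.

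On what is collected, Protocol 5.4 requires that other medications received "during the Treatment and Post-Treatment Follow-Up Periods must be recorded in source documents and on the Concomitant Medication eCRFs". Protocol 5.6 asks that women who stop study drug early stay on the visit schedule unless they withdraw consent, and says of the procedures at withdrawal that "these procedures should not interfere with the initiation of any new treatments or therapeutic modalities that the investigator considers necessary".

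**The concern.** The introductory sentence makes each case sufficient on its own. Case (1) carries a date check; case (2) carries none. A programmer who implements the list as worded will flag every record with a known start and a blank end, including one that began after study drug was finished. The definition one sentence earlier rejects that record.

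At stake is the accuracy of the concomitant-medication table by arm. SAP sections 4.0 and 5.0 plan no per-protocol set and no tabulation of protocol deviations. This table is therefore where a reader would look for on-treatment use of drugs that could affect menses, androgens or metabolic measures. Starts after the last dose are most plausible in women who stop early, so the false entries could differ between arms if early stopping does.

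**Working it through.** The plan states no figure to reproduce here; this is a classification rule. The check applies both rules to the same illustrative records and compares the answers.

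Inputs:
- First dose on Day 1 and last dose on Day 168 (assumed; 24 weeks × 7 days = 168).
- Follow-up to Day 198 (168 + 30 days, from the 30-day period in Protocol 4.1).
- Definition: use up to an end date after the first dose, or ongoing at study end; and start earlier than the last dose.
- Cases: (1) start missing, end on or after first dose; (2) start known, end missing; (3) both missing.
- Ongoing records are entered with a blank end date. This is an assumption, since the documents do not say.

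| Start | End | Definition | Three cases | Case (2) with start before last dose |
|---|---|---|---|---|
| Day −30 | ongoing | concomitant | concomitant | concomitant |
| Day 60 | ongoing | concomitant | concomitant | concomitant |
| Day 168 | ongoing | not | **concomitant** | not |
| Day 180 | ongoing | not | **concomitant** | not |
| Day 180 | unknown | not (fails on start) | **concomitant** | not |
| Day 180 | Day 190 | not | not | not |
| Day −30 | unknown | cannot be decided | concomitant | concomitant |

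The conflict is confined to the three marked rows: start on or after the last-dose day, with no end date. The Day 180 record with an unknown end conflicts however ongoing status is stored. The two ongoing rows conflict only under the storage assumption.

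The last row shows what case (2) is useful for. The start is before treatment, the end is unknown, and use on treatment is possible, so counting it is a sensible convention. Adding the start-date condition leaves that row unchanged and removes only the marked ones.

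Size: with 20 women in an elagolix arm (SAP 2.4), one false entry adds 1/20 = 5 percentage points to a row of the table; in the placebo arm of 30 it adds 1/30 = 3.3 points. Both assume that all randomized women are in the FAS and that the woman is not already counted in that row, since SAP 7.3 counts her once per preferred term. Neither document gives a rate of early stopping or of post-treatment starts, so the number of false entries cannot be derived.

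**The case against.** The strongest reply is that the three cases are missing-date conventions that sit under the definition. Each involves at least one missing date, and the definition already limits the start. On that reading a drug begun after the last dose is never concomitant. The reading is reasonable and may be what was meant, but the text does not say it, and the introductory sentence is worded as sufficient. The contradiction on the page stands. It would be too strong, however, to infer that the SAP has settled on reporting post-treatment drugs as taken during treatment.

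Second, the definition deals with ongoing medications by name, in the same sentence that carries the start-date limit. A reader might infer that every ongoing post-treatment drug falls into case (2). The documents do not support that, because they never equate ongoing with a missing end date. This narrows the certain part of the finding to records with a truly unknown end date.

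Third, a reader might infer that the false entries would mostly be contraceptives, antiandrogens or metformin. SAP 7.3 names no drug, and Protocol 5.3 bars the Table 2 medications through post-treatment follow-up. For women who complete treatment, such use would be a deviation; the more plausible route is early discontinuation. Nothing shows that these drugs would dominate.

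Fourth, counting doubtful records as concomitant is often defended as cautious. That holds where on-treatment use is possible. It does not hold where the known start date is after the last dose.

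**Conclusion.** The point holds as an internal contradiction in SAP 7.3. Followed literally, case (2) misclassifies a medication with a known start after the last dose and no end date. For a start on the last-dose day the two rules merely disagree. Protocol 5.4 and 5.6 show that such records can exist.

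It is minor. The flag feeds counts and percentages only, and no efficacy or safety test uses it. A reader might infer that the primary result could be distorted. The documents point the other way: the primary analysis uses observed cases (SAP 8.3.2), and SAP 8.2 excludes values after premature discontinuation of study drug from that approach. Medication dates are also collected, so a doubtful entry can be checked.

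The only size available is 5 percentage points per false entry in an arm of 20. Any total percentage for an arm would rest on an assumed number of women, and the documents offer no basis for one.

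**What to change.** Either of two edits to SAP 7.3 resolves it:

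- Reword case (2) as: *start date known and prior to the last dose of study drug; end date missing*.
- Or state that the three cases apply only subject to the main definition.

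With either, use the same boundary in both sentences. The definition says prior to the last dose; a case (2) that admitted starts on the last-dose day would leave a smaller version of the same conflict. Also state that ongoing records follow the main definition and are not treated as having a missing end date.

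The cost is one or two sentences in the SAP and the matching condition in the derivation program. No new data are needed. A separate display of medications started after the last dose, or a row for Table 2 drugs by arm, is optional. The latter needs Table 2 mapped to coded drug terms, and neither is required to remove the contradiction.
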